3.2 Tertiary Outcomes

1. Interest in LDKT (lkt_interest): assessed by the question “On a scale of 0-10, with 0 being not at all interested and 10 being extremely interested, how interested do you think you would be in getting a kidney from your family member?”
2. Factual knowledge of LDKT (lktknow1- lktknow10): assessed by 10 factual true/false questions, with a score ranging from 0 (none answered correctly) to 10 (all answered correctly).
3. Perceived knowledge of LDKT (lkt_info11): assessed by the question “How much knowledge do you feel you have now about live donor kidney transplant?” (0=none to 2=a great deal)
4. Knowledge of financial assistance programs: assessed by three questions:
 - a. ldt_info13: Are you aware of any programs that cover the costs of medical evaluations or medical treatment for people who are thinking about donating a kidney or for people who have already donated a kidney?
 - b. ldt_assist1: One program that is available to help people cover the costs of kidney donation is the National Living Donor Assistance Center. There are also state and privately funded programs that can

help. Have you heard of any programs like these before?

- c. ldt_financial2: Is someone you know receiving financial help for donating a kidney on your behalf from a program like this?
- 5. Concerns about LDKT (lkt_concern1- concern9): participants were asked to rate their level of concern in 9 areas of the LDKT process, such as having help after surgery, financial concerns, and guilt and family relationship after donation. Ranges from 0=not at all concerned to 10=extremely concerned.
- 6. Personal financial well-being (pfbws1- pfbws8): 8 questions from the Personal Financial Well- Being Scale (PFWBS) were collected. An average score is calculated across all 8 questions (each ranges from 1 to 10), for a final score ranging from 1 to 10. A score of 1 represents “overwhelming financial distress/lowest financial well-being” and 10 represents “no financial distress/highest financial well-being”.

3.3 Primary Exposure

The primary exposure is the study arm. Usual Care (arm 1) consists of the care participants would normally receive through the Duke Kidney and Pancreas Transplant Program. TALK SWI (arm 2) is a previously developed and validated intervention consisting of “an educational booklet and video coupled with a social worker-led brief behavioral support intervention to help patients and their families overcome barriers to considering and pursuing LDKT.” TALK SWI + FI (arm 3) includes TALK SWI plus a financial assistance intervention “to provide financial support for potential live kidney donors in circumstances where existing federal programs do not provide support.”

4 Statistical Analysis Plan

Exploratory analyses will be performed on the outcomes of interest and distributional assumptions will be checked via histograms, boxplots, and crosstabs. We will also look at the distributions of the outcomes stratified by arm and explore the relationship between the study groups and the outcomes via boxplots and crosstabs. A consort diagram of the flow of participants over the course of the study will be created.

Baseline demographic and clinical characteristics will be presented stratified by study group. No baseline comparisons across study groups will be made. (Table 1 in appendix)

4.1 Analysis Plan for Primary Aim: Live Donor Kidney Activation

Continuous living donor activation at 12 months will be compared across study arms using Kruskal- Wallis test and categorically (if appropriate) using Fisher’s exact test. Similarly, donor inquiries, evaluations, and LDKT will also be compared.

4.1.1 Poisson / ZIP Regression

Note that this section is no longer the main approach and is omitted from the final manuscript.

4.1.1.1 12-month composite activation

The live kidney donor activation score will be compared across study groups using an ANOVA or Kruskal-Wallis test as appropriate. We will then use Poisson regression to determine if the mean rate of activation over 12 months differs by intervention arms. Specifically, we will fit a model of the form

$$g(\mu) = \beta_0 + \beta_1(\text{Arm2}) + \beta_2(\text{Arm3}).$$

Arm2 and Arm3 are indicators of study arm. A Vuong test for comparing non-nested models will be used to test the null that the Poisson and zero-inflated Poisson (ZIP) models are equally close to the true model. If the test rejects in favor of the alternative that the ZIP model is closer, a ZIP will be presented.

In ZIP models, individuals are separated into two groups: those not at risk of an activation (i.e. the excess zeros) with probability ψ , and those who are with probability $1 - \psi$. Then, among those at risk, the activation counts are assumed to be generated from a Poisson process with mean μ . The overall (marginal) distribution of activation score is then

$$Y = \begin{cases} 0 & \text{with probability } \psi \text{ if not at risk} \\ e^{-\mu} \mu^y / y! & \text{with probability } 1 - \psi \text{ if at risk} \end{cases}$$

And the marginal probability function for $P(Y = y)$ is

$$P(Y = 0) = \psi + (1 - \psi)e^{-\mu}$$

$$P(Y = y) = \frac{\psi e^{-\mu} \mu^y}{y!}, \quad y > 0.$$

Denote the prevalence of activation as $\pi = P(Y > 0) = 1 - P(Y = 0) = (1 - \psi)(1 - e^{-\mu})$. Note that the overall mean activation count is $\nu = E(Y) = \mu(1 - \psi)$, and $\text{Var}(Y) = E(Y)(1 + \psi\mu)$, which shows that the variance exceeds the mean when $\psi > 0$. Of primary interest is comparison of the prevalence (π) and overall mean (ν) activation.

The parameter ψ will be modeled by the following logit:

$$\text{logit}(\psi) = \gamma_0 + \gamma_1(\text{Arm2}) + \gamma_2(\text{Arm3}) + \gamma_3(\text{blACT}).$$

blACT is the activation score at randomization (inquiries + evaluations before randomization).

The corresponding Poisson part will be modeled as

$$\log(\mu) = \beta_0 + \beta_1(\text{Arm2}) + \beta_2(\text{Arm3}) + \beta_3(\text{blACT})$$

This models the mean activation counts among those at risk using log-linear models.

4.1.1.2 12-month donor inquiry alone

Similar to activation, donor inquiry will be modeled using Poisson or ZIP as appropriate.

4.1.1.3 12-month donor evaluation alone

Similar to activation, donor evaluation will be modeled using Poisson or ZIP as appropriate.

4.1.1.4 12-month LDKT

Similar to activation, donor inquiry will be modeled using Poisson or ZIP as appropriate.

4.1.2 Primary Approach: Time to First Event Survival Analyses

Note that this section is the PRIMARY approach in the manuscript.

4.1.2.1 12-month composite activation

Outcome: We will use survival analysis techniques to model time to first activation event (inquiry, evaluation, or LDKT) in the presence of two competing risks: deceased donor transplant (DDKT) and death.

Censoring: Participants will be censored if they did not have an activation event during the observation period. Participants with no event before withdrawing from the study will be censored at their withdrawal date; all others with no event will be administratively censored at 12 months after randomization.

Standard survival methods do not work in the presence of competing risks because the assumption that censoring is independent is violated.

Independent censoring means that individuals who are censored have similar risk of the event of interest as those still in the study, but this is not the case for competing risk – if a person dies, that person no longer is at risk of having a donor inquiry or transplant, for example. Standard survival analyses will often overestimate the probability of the event of interest.

The competing risk framework can also be used in our case with nonfatal, semi-competing risks, if interest lies in which event type occurred first. We will use this logic for the analyses of our outcome.

We will use the cumulative incidence function (CIF) to estimate incidence of

occurrence of an activation event in the presence of competing risks. We will also fit subdistribution and cause-specific Cox proportional hazard models. Let $k = 3$ be the number of competing risks: activation event, DDKT, and death. The CIF for the k th event is defined as $\text{CIF}_k(t) = P(T \leq t, K = k)$, the probability of experiencing the k th event before time t and before the occurrence of one of the other events. This will be plotted both overall and by arm.

We will then investigate the subdistribution hazard function, defined as

$$\lambda_k(t) = \lim_{\Delta t \rightarrow 0} \frac{P(t < T \leq t + \Delta t, K = k | T > t \cup (T < t \cap K \neq k))}{\Delta t}$$

This is the “instantaneous *risk of failure* from the k th event in subjects who have not yet experienced an event of type k .” This risk set include those who are event free and *those who have experienced a competing event*.

In contrast, the cause-specific hazard functions for each event is defined as

$$\lambda_k(t) = \lim_{\Delta t \rightarrow 0} \frac{P(t \leq T < t + \Delta t, K = k | T \geq t)}{\Delta t}$$

This is the instantaneous *rate of event k* at time t , in subjects *who have experienced none of the events* (of any type) before time t .

Both subdistribution and cause-specific hazard models will be fit, having the form

$$\lambda_k(t) = \log\{\lambda_{k0}(t)\} + \beta_1(\text{arm2}) + \beta_2(\text{arm3}).$$

Here, $\lambda_{k0}(t)$ denotes the hazard function for participants in arm 1, and “arm2” and “arm3” are indicator variables. Interest lies in β_1 and β_2 , the increased hazard of each event being in the intervention arms compared to the control arm.

4.1.2.2 12-month donor inquiry alone

A similar survival approach described above will be used to model time to first inquiry (ignoring evaluations and LDKTs) in the presence of the competing risks DDKT and death.

4.1.2.3 12-month donor evaluation alone

A similar survival approach described above will be used to model time to first evaluation (ignoring inquiries and LDKTs) in the presence of the competing risks DDKT and death.

4.1.2.4 12-month LDKT

Though it is likely not possible or even meaningful with only 4 events, a similar survival approach will be used to model time to LDKT (ignoring inquiries and evaluations) in the presence of the competing risks DDKT and death.

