3.1 Primary and Secondary Outcomes

1. Live kidney donor activation (primary): per the protocol, “defined as the composite rate of live kidney donor inquiries on behalf of patient participants, completed live kidney donor transplant evaluations, and live kidney donor transplants in each arm, ascertained via medical records maintained by the Duke Kidney and Pancreas Transplant Program.”

In other words: For each participant, the total number of donor inquiries, evaluations, and LDKT over a 12-month period will be summed and defined as the live donor activation score. For example, if a participant had 5 inquiries, 2 evaluations, and an LDKT, then this person’s score would be 8.

In sensitivity analyses, we will look at these individually, and the composite at 24 months.

2. Pursuit of LDKT (secondary) (scenario): Assessed by two questions, Q1: “Has a family member or friend told you that they would give you a kidney?” And Q2: “Have you talked with family and/or friends about the possibility of someone giving you a kidney?”. Participants will be categorized into 3 groups: 3=identified a donor (answered “yes” to Q1); 2=talked with family members/friends but did not identify a donor (“no” to Q1 and “yes” to Q2); 1=did not talk to family members/friends (“no” to Q1 and Q2). Note that once a person has reached a level, he cannot regress to a previous level, e.g., if at level 2 at randomization, the person cannot be at level 1 at month 4.

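### SAP 3.1 defines the primary outcome as a 12-month summed score, but SAP 4.1.2 makes time to first event primary; the analysis kept for the score has no effect estimate, and the switch has no stated date or reason

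*SAP*

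**What the plan says.** - **Outcome definition (SAP 3.1).** After citing the protocol's composite rate, the SAP spells it out: "the total number of donor inquiries, evaluations, and LDKT over a 12-month period will be summed and defined as the live donor activation score". Its worked example has 5 inquiries, 2 evaluations and 1 LDKT, scoring 8. Sensitivity looks at each component and at 24 months are mentioned without an estimator.
- **Tests of the score (SAP 4.1).** "Continuous living donor activation at 12 months will be compared across study arms using" a Kruskal-Wallis test, "and categorically (if appropriate) using" Fisher's exact test. The categories are not defined, and no effect measure or interval is named.
- **Count model (SAP 4.1.1).** A Poisson or zero-inflated Poisson (ZIP) model of the score is set out in full, introduced by: "Note that this section is no longer the main approach and is omitted from the final manuscript". Within it the SAP writes "Of primary interest is comparison of the prevalence" and, in the same sentence, adds the overall mean.
- **Primary analysis (SAP 4.1.2).** "Note that this section is the PRIMARY approach in the manuscript". The outcome is time to the first inquiry, evaluation or LDKT, with deceased donor transplant (DDKT) and death as competing risks. The arm effects are hazard ratios against usual care. Sections 4.1.2.2 to 4.1.2.4 repeat the approach for each component, again to the first event of that type.
- **Protocol.** Section D, Study Outcomes and Assessments, speaks of a composite rate in each arm. Study Phase 2 lists the three events joined by an or. Neither says whether events are summed or only the first counts.

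**The concern.** Two current sections of the SAP describe different primary endpoints. Section 3.1 carries no superseded label, so this is not old text set against new. A hazard ratio for the first event does not estimate a difference in the summed score.

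No model in 4.1.2 counts a second inquiry or a second evaluation. The protocol's background section on identifying donors argues that recipients may have to find several willing donors before one proves eligible, so repeat events are part of what the interventions are meant to produce.

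Once 4.1.1 is left out of the manuscript, a reader would see a hazard ratio for one endpoint and at most p-values for the outcome that 3.1 defines. The SAP also gives no date or reason for the switch. Section 4.1.2.4 already refers to there being four LDKTs, so at least the pooled LDKT total was known when the current text was written. Without a statement of what had been seen, readers cannot judge whether the choice was independent of the results.

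**Working it through.** **What can be reproduced.** The documents give no alpha, power, effect size or event rate, so no power figure can be checked. The stated arithmetic is right: 3 × 100 = 300 participants, and 5 + 2 + 1 = 8.

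**Step 1: the SAP's own example.** A participant scoring 8 and one with a single inquiry on the same day each contribute one event to the composite first-event model, so 7 of the 8 units do not enter it. This is not 7 lost donors, because the score adds stages. If the evaluated donors and the one who donated are among the five who inquired, the score represents five donors, and the model sees the first.

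**Step 2: the SAP's ZIP identities.** Section 4.1.1 gives prevalence π = (1 − ψ)(1 − e^−μ) and mean ν = μ(1 − ψ), hence ν = πμ/(1 − e^−μ). The values of π and μ are assumed, and censoring and competing risks are ignored.
- Equal prevalence π = 0.30: ν = 0.475 at μ = 1 and 0.694 at μ = 2. The mean-score ratio is 1.46 with no difference in the 12-month first-event proportion. The ratio is the same at π = 0.20 (0.316, 0.463) and π = 0.40 (0.633, 0.925).
- Equal mean ν = 0.6: π = 0.6 × 0.632 = 0.379 at μ = 1, and π = 0.3 × 0.865 = 0.259 at μ = 2. The approximate subdistribution hazard ratio is ln(1 − 0.259)/ln(1 − 0.379) = 0.63 with no difference in mean score.

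**Step 3: hand approximation of power.** Assume 100 per arm, two-sided 5%, and a score of 1 + Poisson(e) in activated participants, with share p.
- First event: HR = ln(1 − p₃)/ln(1 − p₁), SE = √(1/(100p₁) + 1/(100p₃)).
- Score: mean m = p(1 + e), squared coefficient of variation c = [e + (1 + e)²]/[p(1 + e)²] − 1, SE of the log rate ratio = √((c₁ + c₃)/100).

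Results:
- *Share only, 30% to 45%, e = 0.5.* HR = 0.598/0.357 = 1.68, SE 0.236, z = 2.19, power 59%. Rate ratio 0.675/0.45 = 1.5, c = 3.07 and 1.72, SE 0.219, z = 1.85, power 46%.
- *Events per activated participant only, p = 35%, e from 0.5 to 2.0.* HR = 1, so power is 5% by construction. Rate ratio 1.05/0.525 = 2, c = 2.49 in both arms, SE 0.223, z = 3.10, power 87%.
- *Both, p from 30% to 40%, e from 0.5 to 1.0.* HR = 1.43, SE 0.242, z = 1.49, power 32%. Rate ratio 0.80/0.45 = 1.78, SE 0.228, z = 2.52, power 71%.

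**Step 4: simulation with competing events.** Assumed: three arms of 100, arm 3 effective, 8% DDKT, 5% death. The score is counted up to DDKT, death or 12 months. The baseline activation score (blACT in 4.1.1.1) is correlated with risk. There were 4,000 runs (standard error at most 0.8 points). First event is a cause-specific Cox model; the count is a log-linear model with arm terms, blACT and robust standard errors; Kruskal-Wallis is across three arms.

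| Case | First event | Count | Kruskal-Wallis |
|---|---|---|---|
| Events per activated only (0.5 to 2.0 extra), share 25 / 35 / 50% | 5 / 5 / 5% | 66 / 82 / 97% | 9 / 17 / 48% |
| ZIP, ψ unchanged, μ doubled from 0.874, control share 25 / 35 / 50% | 37 / 57 / 88% | 75 / 91 / 99% | 50 / 77 / 99% |
| Share only, 30 to 45% | 60% | 45% | 58% |
| Both, 30 to 40% and 0.5 to 1.0 extra | 32% | 70% | 48% |

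At 35% in the first two cases, the fraction of score units that the composite model does not use (1 − activated share/mean score) is 33–34% in usual care and 53–66% in the effective arm. At 35% under the null, the median 95% CI factors are ×/÷1.58 for the rate ratio and ×/÷1.63 for the hazard ratio, so the count is about as precise here.

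**The case against.** The case for the plan as it stands is fair in several respects.

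- *First event is a legitimate reading.* The protocol's or-list fits it, prevalence was one of the two quantities of interest in 4.1.1, the cumulative incidence curves retain it, and 4.1.2 handles DDKT and death explicitly, which the score definition does not. This stands, and it is why first event may remain primary. It does not reconcile 4.1.2 with 3.1.
- *The score does have a model.* A reader might infer that the SAP contains no effect estimate for the score at all. That goes too far: the Poisson/ZIP model is still printed, and the appendix tables are not in the text available. The narrower statement holds: the analysis text kept for reporting specifies tests only.
- *The change is labelled.* The SAP openly marks the superseded and primary sections. A reader might still infer from the reference to four LDKTs that the switch was driven by results. The documents do not support that: a pooled count of one rare component says nothing about results by arm. Section 4.1.2.1 does give reasons, but for competing-risk methods over standard survival methods, not for first event over the count.
- *The protocol carries a later date and no time-to-event wording.* A reader might take this as evidence against the switch. It is not: the supplied protocol has no statistical analysis section, and its population section still uses January 2014 figures.
- *The power figures rest on assumed inputs.* True. The 5% in the first case is simply the error rate, since nothing that the model can see has changed.

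**Conclusion.** The conflict is real and rests on current text alone: 3.1 and 4.1.2 do not describe the same primary endpoint, the reported analysis gives the summed score no effect size, and the switch has no stated date or reason. The example in 3.1 and the ZIP identities in 4.1.1 are enough to show that the two endpoints can disagree in either direction.

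The size depends on assumed activation shares, event counts, DDKT and death rates, none of which the documents give. Within the range examined, neither analysis dominates. The count is far stronger when activated participants attract more events. First event is stronger when only the activated share changes.

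No bias, error inflation or wrong formula in the first-event analysis has been shown here, and the choice of first event is not itself a fault. This should be fixed, as a matter of estimand and disclosure; it is not a defect that invalidates the trial's primary comparison.

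**What to change.** 1. **Name one primary estimand in both 3.1 and 4.1.2.** First event may stay primary. Beside it, report the 12-month score with each intervention arm's rate ratio against usual care and a 95% CI, from a log-linear model with arm terms, blACT and robust standard errors. This is a small change to the Poisson model in 4.1.1.1. Keep Kruskal-Wallis as a check. State how DDKT, death and withdrawal before 12 months enter the score.
2. **Disclose the change.** State when and why the approach moved from the count to first event, which data had been seen, and by whom. Label the restored count analysis as supportive and specified after data.
3. **Optional.** Add blACT to the hazard models as a sensitivity analysis. Randomisation already protects the unadjusted contrast, and the gain may be small: in the share-only case, power went from 61% to 64% in a separate set of 3,000 runs, and from 60% to 75% with a strongly prognostic blACT.

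The cost is wording plus one modified model on data already collected; sample size and alpha do not change. There are downsides. The score is skewed, and a heavier tail than assumed would widen its interval. One donor who inquires, is evaluated and donates counts three times. The count has less power when only the activated share changes.

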- s) The patient participants and family/friend participant(s) will then meet/talk with the study Social Worker for up to one hour. The session will be audio recorded (**In-person SWI:** encrypted audio voice recorder; **Telephone SWI:** encrypted audio voice recorder using speakerphone in a GIM private office) as described in their consents, but if they refuse to be audio recorded, the session will continue and only handwritten notes will be taken by the study Social Worker.
- t) **In-person SWI:** Study staff will administer a brief 10-minute hardcopy questionnaire to the patient participant immediately following the Social Worker session to obtain feedback about the acceptability of the TALK SWI. We will provide assistance with reading the questions and checking the responses if needed. **Telephone SWI:** Once the SWI session is complete, the Social Worker will ask the patient participant to remain on the line to complete their post assessment and paperwork for payment. They will remind the family/friends that Study Staff will contact them shortly to complete their post assessment and paperwork for payment. The Social Worker will leave the call and immediately notify one of the other study staff to join the call. The Study Staff will 1) administer the brief 10-minute questionnaire, and 2) complete the paperwork required for payment. If consented family/friends attended, the Study Staff will call the family/friends to 1) administer the brief 10-minute questionnaire, and 2) complete the paperwork required for payment.
- u) Study staff will mail patient participants a thank you note and \$50 check for completing the session with the family/friend participant(s) and study Social Worker.

2. Assessments

- v) All patient participants (regardless of their random assignment) will be contacted at 4 and 12 months to complete follow up questionnaires via telephone. Study staff will mail a thank you note and \$30 check for completion of each of the questionnaires. All questionnaires are approximately 60 minutes in length.
- w) All patient participants will be followed for 2 years (post baseline questionnaire completion) via electronic medical records (i.e., MaestroCare and DKPTP PHX reporting system) to passively assess live kidney donor activation on their behalves (live donor inquiries, completed new live donor evaluations, or live kidney donation) as well as their status on their wait list (active/inactive).

B. Family/Friend Participants

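### The primary time-to-event analysis censors at study withdrawal without separating loss of contact from loss of record permission, so it can discard activation events that the clinic records still capture

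*SAP*

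**What the plan says.** SAP 4.1.2 is headed as the primary approach and adds: "Note that this section is the PRIMARY approach in the manuscript". Under Censoring, 4.1.2.1 has two rules. The one at issue reads "Participants with no event before withdrawing from the study will be censored at their withdrawal date", and the other reads "all others with no event will be administratively censored at 12 months after randomization". Withdrawal is not defined by type.

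The source of the outcome is stated separately. SAP 3.1 has inquiries, evaluations and transplants "ascertained via medical records maintained by the Duke Kidney and Pancreas Transplant Program". The Protocol (Design and Procedures, D. Study Outcomes and Assessments) says transplant coordinators log donor inquiries as part of routine work. The Protocol's Assessments for patient participants, item w, states: "All patient participants will be followed for 2 years (post baseline questionnaire completion) via electronic medical records". The purpose given is "to passively assess live kidney donor activation on their behalves". That item makes no exception for participants who withdraw.

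SAP 4.1.2.1 also gives the condition under which censoring is harmless: "Independent censoring means that individuals who are censored have similar risk of the event of interest as those still in the study". It uses this to justify treating death and deceased-donor transplant as competing risks. It does not apply it to withdrawal.

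**The concern.** Stopping questionnaires or social worker sessions does not prevent a donor from calling the program, being evaluated or donating, and it does not prevent the program from recording this. For such a participant, censoring at withdrawal throws away information that the study's own follow-up plan would collect.

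Two things are at stake. One is precision, because any activation after withdrawal is lost. The other is validity. Censoring assumes that withdrawers would have activated at the same rate as those who stayed. If their rate differs and withdrawal is more common in one arm, the risk sets stop being comparable. Unequal withdrawal is plausible, since only Arms 2 and 3 are asked to review materials and attend two meetings about LDKT. The sensitivity analyses in SAP 3.1 (single components, and the composite at 24 months) do not test this assumption.

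**Working it through.** **No plan figure to reproduce.** The documents give 100 participants per arm and a 12-month window. They give no withdrawal rate, expected activation rate or effect size. Everything below that needs one of these is an assumption.

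**Assumptions.** Two arms are compared and there is no true effect. The 12-month activation probability is 30% and that of competing events is 10%, both with constant hazards. A share *q* of participants, the same in both arms, belongs to a class with *r* times the activation hazard of the rest. All of that class withdraws in the intervention arm and a quarter of it in usual care, uniformly over months 0.5 to 4.

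**Hand check of the limit.** Once the class has left, intervention participants have relative hazard 1. Those left in usual care average

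[(1 − q) + 0.75·q·r] / (1 − 0.25·q),

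and the spurious hazard ratio is the inverse.

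- q = 0.20, r = 0.25: (0.80 + 0.0375)/0.95 = 0.882, so HR = 1.13.
- q = 0.20, r = 2: (0.80 + 0.30)/0.95 = 1.158, so HR = 0.86.
- q = 0.05, r = 0.25: (0.95 + 0.0094)/0.9875 = 0.972, so HR = 1.03.
- r = 1: the ratio is 1 for every q.

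These are limits. The class is at risk until it leaves, and a high-hazard class is also used up faster, so the actual shift is smaller.

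**Simulation.** A cause-specific Cox model with an arm indicator, 2,000,000 participants per arm, censored at withdrawal:

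| Intervention withdrawal | r = 0.25 | r = 0.5 | r = 1 | r = 2 |
|---|---|---|---|---|
| 5% | 1.03 | 1.01 | 1.00 | 0.98 |
| 10% | 1.05 | 1.03 | 1.00 | 0.96 |
| 20% | 1.12 | 1.07 | 1.00 | 0.92 |

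The same simulated participants followed to 12 months give 1.00 in every cell.

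**Harsher assumptions.** Suppose withdrawal occurs in the intervention arm only, control activation is 20% or 40%, and withdrawers range from almost no activation to twice the hazard. The hazard ratio then spans 0.88 to 1.25. In the most extreme null case (40% activation, 20% withdrawal, almost no activation among withdrawers), type I error at 100 per arm is about 13%, against 4% with full follow-up.

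**Events lost when withdrawal is unrelated to activation.** At 20% withdrawal and an average exit at month 2.25, the loss per 100 is about 100 × 0.20 × 0.30 × (12 − 2.25)/12 = 4.9, or 4.4 in the simulation once competing events are allowed for. With equal withdrawal in both arms and 20–40% activation, the loss is about 1.5–3 per 100 at 10% withdrawal and 3–6 per 100 at 20%.

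**Scale against sampling error.** With about 30 events per arm, SE(log HR) ≈ √(1/30 + 1/30) = 0.26. A shift to 1.12 is ln(1.12)/0.26 = 0.44 SE. Two-sided type I error is then about Φ(−1.52) + Φ(−2.40) = 0.064 + 0.008, or 7%. A shift to 1.05 is 0.19 SE, or about 5.4%.

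The subdistribution model and the cumulative incidence curves were not simulated. They use the same censoring date.

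**The case against.** The strongest reply is that withdrawing from the study may already mean complete withdrawal. Elsewhere the documents treat non-participation differently: missed sessions are rescheduled or offered by telephone, missing questionnaires are handled by imputing zero steps (SAP 4.2.3), and participants may decline any part of the study. On that reading, people who only stop contact fall under the 12-month rule, and the remedy mostly restates current intent. This is a fair reading, but the SAP does not state it. The primary analysis should not rest on an undefined term, and if this reading is right the clarification changes nothing.

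Second, consent text is not in the public documents, so whether records may be used after withdrawal cannot be checked. This stands. Where record permission is revoked, censoring at that date is appropriate.

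Third, SAP 3.1 and 4.1 already compare 12-month event totals by Kruskal-Wallis test with no withdrawal cut-off. This helps, but that comparison is not the primary one, and the plan does not say whether it counts post-withdrawal events.

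Fourth, the effect is small under moderate assumptions, as the comparison with sampling error shows. This also stands.

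A reader might infer that the bias must favour the interventions. The documents do not support that. Arms 2 and 3 carry more burden but also offer $50 per session and a telephone option, and nothing says whether withdrawers are more or less likely to activate. A reader might also infer that the rule abandons analysis as randomised. It does not: withdrawers stay in their assigned arm and contribute time until censored.

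**Conclusion.** The point holds as a defect in the wording of the primary censoring rule. It does not show that the result is biased. The rule as written merges two kinds of withdrawal, and for people who only stop contact it discards outcomes that the follow-up plan is built to capture.

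The loss of events needs no assumption about why people withdraw, only that some of them later activate. Bias needs more: withdrawal must be related to activation and differ by arm. Under the assumed range (5–20% intervention withdrawal, a quarter as much in usual care, 0.25–2 times the hazard), a null hazard ratio moves to about 0.92–1.12. It does not move at equal hazards, and moves by about 0.03 or less at 5% withdrawal. The true number of withdrawals is not stated and could be close to zero. That later outcomes are obtainable is established only for participants whose record permission survives. The change is worth making because it is cheap and removes an untested assumption from the primary analysis.

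**What to change.** Replace the withdrawal sentence in SAP 4.1.2.1 with:

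> Participants who stop sessions or questionnaires remain under medical-record ascertainment and are administratively censored at 12 months; only participants who revoke permission to use their records are censored, at the revocation date.

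Add withdrawals by arm and type to the CONSORT diagram, and keep the current rule as a sensitivity analysis. SAP 4.1.2.4 already cites the number of LDKT events, so the change should be dated and both results reported.

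The cost is one sentence, a withdrawal-type flag and one extra model run. The records are already planned to be pulled for all patient participants. The downside is that each withdrawn participant's consent status must be checked before later records are used.
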